#### IAP Measurements of Interest:

- 1) Baseline level prior to the start of the procedure
- 2) One Intraoperative measurement
- 3) Following evacuation of pneumoperitoneum and closure of surgical wounds
- 4) During extubation process

During the surgery, lactic acid levels will be measured utilizing the StatStrip Lactate Monitor. In serial fashion, a small aliquot of blood will be collected for rapid, point-of-care analysis. These values will then be recorded and input into the database upon completion of the surgery.

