For this study, we will evaluate obese individuals who are undergoing laparoscopic inguinal hernia repair. Utilizing the novel technology of the Accuryn Monitoring System and StatStrip Lactate Meter, we will continuously assess IAP, urine output, and lactic acid levels throughout the surgery. Due to the technology's novel means of measurement, we believe our study will provide more precise and accurate measurements of IAP as the Accuryn Monitoring System eliminates the requirement of bladder distention for pressure measurement. Indirectly measuring IAP via intravesicular pressure measurements has been demonstrated by numerous studies to be both accurate and effective. Furthermore, it is our aim to better understand the fluctuations in IAP that occur in obese individuals during the peri-operative setting and how those fluctuations impact organ dysfunction. With the ability to continuously monitor urine output and obtain accurate, rapid lactate levels, we believe our study will demonstrate a measurable correlation between these two values. The role of obesity in inguinal hernia recurrence has been debated as some studies have argued patients with higher BMIs have higher likelihood of recurrence, whereas others have shown obesity as more of a "protective" factor. By examining the changes of IAP during extubation, we hope to gain further insight into IAP physiology and how we can use these measurements to guide our patients in the post-operative setting. To our knowledge, this is the first time this technology will be used in this capacity and it will be the first time IAP will be monitored in a completely continuous fashion.

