## **STUDY OBJECTIVES AND HYPOTHESIS**

Our study aims to better understand the physiology of intraabdominal pressure (IAP) in obese individuals undergoing minor ambulatory surgery. During this study, we will attempt to further our knowledge of IAP and its role in hernia recurrence, as well as the complexities of lactic acid levels and urine output in the setting of elevated IAP. In patients undergoing inguinal hernia repair, intraabdominal pressure has been implicated as a factor placing patients at increased risk of hernia recurrence. In some scenarios, hernia repairs are placed under tremendous strain immediately upon completion of the repair during extubation. Which has led to the following questions; What are the levels of IAP reached in obese individuals during extubation following laparoscopic inguinal

hernia repair? How do the IAP levels compare to previously measured levels in individuals performing everyday activities and strenuous movements?

These questions have led us to formulate the following hypotheses:

Hypothesis #1: Obese individuals will demonstrate significantly elevated IAP during extubation.

Hypothesis #2: The IAP in obese individuals during extubation will be elevated in comparison to levels previously reported during everyday activities and strenuous movements.

In the critical care world, IAP has garnered attention in the setting of abdominal compartment syndrome and subsequent organ dysfunction. Historically, lactic acid and urine output have been used as barometers of organ dysfunction. However, researchers have had difficulty demonstrating a correlation between the two metrics as technology previously limited the capabilities of investigators to precisely and accurately compare the two. During this study we will utilize novel technology to monitor lactic acid and urine output in a “real-time” fashion in the hopes of addressing the following questions. Do temporary elevations in IAP during minor ambulatory surgery elicit systemic organ dysfunction in obese individuals? Is there a measurable association between changes in lactic acid and urine output induced by insufflation during laparoscopic surgery?

To address these questions, we hypothesize:

Hypothesis #3: Obese individuals undergoing minor laparoscopic surgery will develop significant elevations in lactic acid and decreases in urine output.

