## **STUDY DESIGN**

This research will be conducted as a prospective, observational study with the intention of serving as a “pilot” study to explore the opportunity for further research inquiries. The observational model is sufficient for this project as it will allow us to collect information in our setting/environment of interest.

The study will be conducted at Maimonides Medical Center and Maimonides Medical Center IRB approval will be obtained prior to proceeding. A total of 25 individuals will be recruited in the outpatient setting for enrollment into the study. Target patients will be those individuals that present in the outpatient office for surgical consultation regarding inguinal hernia. Patients will be approached for inclusion in the study if they are adults between the ages of 18-65, obese (BMI >30), have a diagnosis of inguinal hernia, and qualify for laparoscopic inguinal hernia repair. Patients will not be approached for the study if they satisfy any of the exclusion criteria, which includes previous resections resulting in short bowel, extensive abdominal scarring, BMI < 30, fall outside the designated age parameters, or fail to qualify for a laparoscopic hernia repair. If patients qualify and

agree to participate in the study, informed consent will be obtained prior to scheduling the surgery. We anticipate it will take approximately 1-2 months for patient recruitment.

Sample size was guided by previous studies in the literature that have examined IAP in patients. This number of individuals will allow for sufficient data collection to identify points of interest for future projects. Additionally, in an effort to conduct this study in a reasonable time frame, previous case volume indicated it would be reasonable to recruit 25 individuals within the desired time frame.

For this project there is no indication to conduct a power analysis as this project will remain purely observational in nature with the purpose of serving as a pilot study. The goal of this study is not to make any practice changing conclusions, but rather to identify findings that will warrant further investigation on a larger scale.

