#### Timing of Lactic Acid Measurements:

- 1) Baseline level following intubation and induction but prior to start of the procedure
- 2) Every 10 minutes during the surgery
- 3) During extubation process
- 4) 30 minutes postoperatively
- 5) 60 minutes postoperatively

A summary of the study steps is provided:

- 1) Identify patients for laparoscopic inguinal hernia repair
- 2) Enroll, Consent patient for study, and schedule surgery
- 3) Collect patient demographic data
- 4) Preadmission Testing and Routine Preoperative Laboratory Testing
- 5) Peri-operative patient preparation
- 6) Insertion of Foley catheter and connect to Accuryn Monitoring System
- 7) Measurement of baseline intraabdominal pressure and lactic acid level
- 8) Begin laparoscopic inguinal hernia repair
- 9) Intraoperative measurement of intraabdominal pressure, urine production/output, and serial lactic acid levels
- 10) Upon completion of repair, completely evacuate pneumoperitoneum and closure of surgical wounds
- 11) Measure IAP for return to baseline IAP measurement obtained at start of procedure
- 12) Proceed with extubation, IAP measurement, and lactic acid level

- 13) Upon extubation, disconnect Foley catheter from Accuryn Monitoring System and remove from patient
- 14) Measurement of 30 min and 60 min post-operative lactic acid levels

Post operatively patient care will proceed in the usual fashion. Patients will be monitored for a duration of time in the post-anesthesia care unit as deemed appropriate by the anesthesia team prior to discharge home. Patients will be seen in the office two weeks following their surgery for follow up.

Prior to the procedure, the anesthesia team will be informed of our intention to have the patient extubated following closure of all surgical wounds with the intention of recording intraabdominal pressure during the process of extubation. The anesthesia team will otherwise be asked to proceed with extubation as per their usual protocol. If at any point the anesthesiologist determines there is an increased level of risk to the patient as a result of this study protocol, then the study will be aborted, and data collection terminated for patient safety.

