As a result of the Accuryn Monitoring System's technology, data will be collected in a continuous fashion. A member of the study team will be present during the surgery and will help record the IAP measurements of interest during the corresponding portion of the procedure. Measurements will be confirmed with the operating surgeon prior to proceeding with the next step. During the surgery, study staff will also be responsible for collecting blood samples and utilizing the StatStrip Lactate Monitor to measure lactic acid levels at appropriate time intervals as per study protocol. During the surgery data will be collected using the Data Collection Worksheet. Upon completion of the surgery, data will be transferred from the worksheet into the database and the worksheet will subsequently be destroyed.

Data will be input and stored in the study database following completion of the surgery. The database will be constructed prior to the start of the study and will be the primary storage location for demographic and intraoperative data. Data that is input into the database will be deidentified so as to protect patient privacy. Upon completion of data collection, data will be analyzed for values of significance and results will be compared to previously published values of IAP obtained during various activities and "strenuous movements".

[name], a biostatistician, will perform the data analysis. All continuous variables will be checked for symmetry and summarized with mean and standard deviation if symmetry is upheld. Groups will be compared using the t-test. If symmetry is not upheld, then medians and IQR will be used to summarize, and a Wilcoxon test used to determine group differences. All categorical variables will be summarized with frequency and percent, and groups will be compared with a chi-square, or a fisher exact test where necessary. Results of the analysis will be used to compose a manuscript with the goal of being published in a peer reviewed journal.

Upon completion of the study, all data collected during the study will be destroyed. The master list will be destroyed, and the project database will be deleted.

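### No planned analysis relates intraabdominal pressure to lactate or urine output, and the plan does not say how the continuous pressure trace will be stored or summarised

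*Combined protocol and SAP*

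**What the plan says.** **Aim.** The Background and Significance section wants to understand IAP fluctuations around surgery and "how those fluctuations impact organ dysfunction". Study Objectives and Hypothesis asks: "Do temporary elevations in IAP during minor ambulatory surgery elicit systemic organ dysfunction in obese individuals".

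**Hypotheses.** Hypothesis #3 reads "Obese individuals undergoing minor laparoscopic surgery will develop significant elevations in lactic acid and decreases in urine output"; IAP is not a term in it. Hypothesis #4 attributes the lactate and urine changes to raised IAP, but the association it predicts is between lactate and urine output. Expected Outcomes repeats that pairing.

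**Measurement.** Study Design says that the bladder-catheter monitor measures IAP continuously and lists four points of particular interest: baseline, "One Intraoperative measurement", after wound closure, and extubation. Lactate is taken at baseline, "Every 10 minutes during the surgery", at extubation, and 30 and 60 minutes after surgery. Urine output is listed as an intraoperative measurement, with no interval or summary given.

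**Data flow.** A team member records the IAP points of interest. Data from surgery go onto a worksheet and from there into the database, and the worksheet is then destroyed. All study data are destroyed when the study ends.

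**Analysis.** The analysis paragraph of Study Design gives means or medians, then "Groups will be compared using the t-test" or a Wilcoxon test, and chi-square or Fisher tests for categorical data. IAP is also to be compared with published values. No correlation, regression or repeated-measures method is named.

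**The concern.** The question is about exposure and response: does more IAP go with more lactate or less urine? The plan measures both sides and never connects them. If lactate rises and urine falls during surgery, the wording of Hypothesis #4 invites the reader to credit IAP, without any check that patients or intervals with higher IAP changed more.

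The named readings would not support that check. One untimed value cannot describe fluctuation or duration, and it cannot be matched to a particular lactate sample.

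Timing matters too. The worksheet is the only route to the database that the plan describes, and all data are destroyed at the end. If the trace is not exported and aligned while patients are being studied, the relationship may not be recoverable afterwards.

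**Working it through.** The plan states no effect size, standard deviation, alpha or power for this question, so there is no figure to reproduce. The check is a comparison of the text followed by two short illustrations.

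**1. Aim against analysis**

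| Element | Relates IAP to lactate or urine output? |
|---|---|
| Background aim; question in Study Objectives | Yes, as a question |
| Hypotheses #1 and #2 | No; IAP alone, or IAP against published levels |
| Hypothesis #3 | No; lactate and urine output, without IAP |
| Hypothesis #4; Expected Outcomes | No; lactate against urine output |
| Analysis paragraph | No; summaries, group tests, published IAP values |

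The groups in the analysis paragraph are not defined, and the study has one cohort: "A total of 25 individuals will be recruited in the outpatient setting for enrollment into the study". Paired tests are not specified either.

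**2. Readings available**

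Operating time is not in the documents, so it is assumed. Lactates during surgery = minutes / 10. Total lactates = that number + 4 (baseline, extubation, 30 and 60 minutes). Named IAP points are always 4, with 1 during surgery.

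| Assumed duration | Lactates during surgery | Named IAP during surgery | Total lactates | Total named IAP |
|---|---|---|---|---|
| 30 min | 3 | 1 | 7 | 4 |
| 60 min | 6 | 1 | 10 | 4 |
| 90 min | 9 | 1 | 13 | 4 |
| 120 min | 12 | 1 | 16 | 4 |

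Baseline and extubation appear in both schedules. The intraoperative IAP reading has no stated time, so it pairs with no particular lactate.

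**3. Where interval data can exist**

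In the summary of study steps, the catheter is disconnected and removed on extubation (step 13), before the 30- and 60-minute lactates (step 14). IAP and urine data therefore cover only the intervals from baseline to extubation. For an assumed 60-minute operation that is 6 + 2 = 8 draws, or 7 intervals per patient if no two draws coincide.

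**4. What 25 patients can show**

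Assume one IAP summary and one lactate or urine change per patient, 25 complete, two-sided alpha 0.05. By Fisher's z the standard error is 1/√(25 − 3) = 0.213, and the 95% interval is tanh(atanh(r) ± 1.96 × 0.213).

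- r = 0: -0.40 to 0.40
- r = 0.3: -0.11 to 0.62
- r = 0.5: 0.13 to 0.75

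The correlation detectable with 80% power is tanh((1.96 + 0.84)/√22) = 0.54. Power is 31% at r = 0.3, 51% at 0.4 and 73% at 0.5. These figures are for a between-patient correlation. They do not give the precision of a repeated-measures slope, which depends on variance components that the documents do not give.

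**5. IAP and elapsed time**

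If IAP sits a constant P above baseline for t minutes, the cumulative area above baseline is P × t. Within a patient that is proportional to elapsed time, so the two cannot be told apart. Interval mean IAP does not grow with time in this way. However, if pressure is nearly constant during insufflation, its within-patient contrast comes mainly from intervals with and without insufflation.

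**The case against.** The strongest defence has three parts.

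**The trace exists.** Study Design says twice that collection is continuous, and calling four points of particular interest does not say that the rest is dropped. This stands. A reader might infer that IAP is kept as a single intraoperative value; the documents do not say so. They are silent on storing, exporting and summarising the trace, and that silence is the gap.

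**Hypothesis #3 gives some answer.** Lactate is drawn before, during and after surgery in the same patients, and IAP is checked for return to baseline after closure. This stands in part. A reader might infer that the question gets no answer at all, which is too strong. But the evidence is indirect: anaesthesia, surgery and elapsed time change over the same period, and nothing is learned about the size or fluctuation of IAP.

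**It is a pilot.** The plan says "there is no indication to conduct a power analysis as this project will remain purely observational in nature" and disclaims practice-changing conclusions. That answers any demand for a powered test. It does not explain leaving out an estimate of a relationship that the study set out to explore.

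It is also tempting to attach a percentage loss from using one reading in place of many. The documents do not support one. They fit no slope that could be diluted, and they give no within- or between-patient variance and no correlation between successive readings.

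**Conclusion.** The point holds in this form: a stated question about IAP and organ function has no planned analysis that uses IAP as an explanatory variable, the named intraoperative reading is single and untimed, and handling of the continuous trace is unspecified. Following the plan as written gives indirect evidence only.

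The mismatch is one named IAP reading against 3 to 12 lactates during surgery, for assumed operating times of 30 to 120 minutes. No bias can be put on a planned result, because no planned result uses IAP in this way. The absence of an IAP analysis rests on the text alone; the reading counts rest on the assumed durations, and the precision figures on 25 complete patients and one summary each. The change is worth making before enrolment, but the analysis it adds can only be exploratory.

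**What to change.** 1. **Keep the four named IAP readings**, and record the time of the intraoperative one.
2. **Export the continuous IAP and urine record** to the study database, with lactate draw times on the same clock. State this in the data-handling text of Study Design.
3. **Derive exposure by interval.** For each interval between lactate draws, from baseline to extubation only, compute the time-weighted mean IAP above baseline. As a secondary measure, compute the area above baseline (that mean × interval length).
4. **Add one exploratory repeated-measures model to the analysis paragraph**, fitted once for interval lactate change and once for interval urine rate: outcome = intercept + patient random intercept + β₁ × interval mean IAP above baseline + β₂ × elapsed time + error. Report β₁ with a 95% confidence interval, as an association.
5. **Report the 30- and 60-minute lactates descriptively**; they have no concurrent IAP or urine data.

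**Cost.** Exporting, storing and aligning the trace, and one model form applied to two outcomes. No extra patients, samples or procedures are needed. Slopes will be imprecise with 25 patients, and cumulative IAP may be hard to separate from elapsed time if pressure is nearly constant during insufflation. The report should state both limits.

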#### Timing of Lactic Acid Measurements:

- 1) Baseline level following intubation and induction but prior to start of the procedure
- 2) Every 10 minutes during the surgery
- 3) During extubation process
- 4) 30 minutes postoperatively
- 5) 60 minutes postoperatively

A summary of the study steps is provided:

- 1) Identify patients for laparoscopic inguinal hernia repair
- 2) Enroll, Consent patient for study, and schedule surgery
- 3) Collect patient demographic data
- 4) Preadmission Testing and Routine Preoperative Laboratory Testing
- 5) Peri-operative patient preparation
- 6) Insertion of Foley catheter and connect to Accuryn Monitoring System
- 7) Measurement of baseline intraabdominal pressure and lactic acid level
- 8) Begin laparoscopic inguinal hernia repair
- 9) Intraoperative measurement of intraabdominal pressure, urine production/output, and serial lactic acid levels
- 10) Upon completion of repair, completely evacuate pneumoperitoneum and closure of surgical wounds
- 11) Measure IAP for return to baseline IAP measurement obtained at start of procedure
- 12) Proceed with extubation, IAP measurement, and lactic acid level

- 13) Upon extubation, disconnect Foley catheter from Accuryn Monitoring System and remove from patient
- 14) Measurement of 30 min and 60 min post-operative lactic acid levels

Post operatively patient care will proceed in the usual fashion. Patients will be monitored for a duration of time in the post-anesthesia care unit as deemed appropriate by the anesthesia team prior to discharge home. Patients will be seen in the office two weeks following their surgery for follow up.

Prior to the procedure, the anesthesia team will be informed of our intention to have the patient extubated following closure of all surgical wounds with the intention of recording intraabdominal pressure during the process of extubation. The anesthesia team will otherwise be asked to proceed with extubation as per their usual protocol. If at any point the anesthesiologist determines there is an increased level of risk to the patient as a result of this study protocol, then the study will be aborted, and data collection terminated for patient safety.

As a result of the Accuryn Monitoring System's technology, data will be collected in a continuous fashion. A member of the study team will be present during the surgery and will help record the IAP measurements of interest during the corresponding portion of the procedure. Measurements will be confirmed with the operating surgeon prior to proceeding with the next step. During the surgery, study staff will also be responsible for collecting blood samples and utilizing the StatStrip Lactate Monitor to measure lactic acid levels at appropriate time intervals as per study protocol. During the surgery data will be collected using the Data Collection Worksheet. Upon completion of the surgery, data will be transferred from the worksheet into the database and the worksheet will subsequently be destroyed.

Data will be input and stored in the study database following completion of the surgery. The database will be constructed prior to the start of the study and will be the primary storage location for demographic and intraoperative data. Data that is input into the database will be deidentified so as to protect patient privacy. Upon completion of data collection, data will be analyzed for values of significance and results will be compared to previously published values of IAP obtained during various activities and "strenuous movements".

[name], a biostatistician, will perform the data analysis. All continuous variables will be checked for symmetry and summarized with mean and standard deviation if symmetry is upheld. Groups will be compared using the t-test. If symmetry is not upheld, then medians and IQR will be used to summarize, and a Wilcoxon test used to determine group differences. All categorical variables will be summarized with frequency and percent, and groups will be compared with a chi-square, or a fisher exact test where necessary. Results of the analysis will be used to compose a manuscript with the goal of being published in a peer reviewed journal.

Upon completion of the study, all data collected during the study will be destroyed. The master list will be destroyed, and the project database will be deleted.

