Hypothesis #4: Changes in lactic acid and urine output caused by IAP elevation in obese individuals will demonstrate a measurable association.

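### Hypotheses 3 and 4 rest on a change in urine output, but the plan defines no pre-insufflation urine rate to measure the change from

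*Combined protocol and SAP*

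**What the plan says.** Hypothesis 3 (STUDY OBJECTIVES AND HYPOTHESIS) states: "Obese individuals undergoing minor laparoscopic surgery will develop significant elevations in lactic acid and decreases in urine output". Hypothesis 4 states: "Changes in lactic acid and urine output caused by IAP elevation in obese individuals will demonstrate a measurable association". Both concern a change in urine output.

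The numbered summary of study steps in STUDY DESIGN handles urine as follows:

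- Step 6, before surgery: "Insertion of Foley catheter and connect to Accuryn Monitoring System".
- Step 7, baseline: "Measurement of baseline intraabdominal pressure and lactic acid level". Urine output is not listed.
- Step 9: "Intraoperative measurement of intraabdominal pressure, urine production/output, and serial lactic acid levels". This is the only step that names urine.
- Step 13: "Upon extubation, disconnect Foley catheter from Accuryn Monitoring System and remove from patient".
- Step 14: "Measurement of 30 min and 60 min post-operative lactic acid levels".

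IAP has its own list of four measurement points and lactate has a list of five timing entries. Urine output has no such list, and no interval, unit or definition of change.

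BACKGROUND AND SIGNIFICANCE says that "we will continuously assess IAP, urine output, and lactic acid levels throughout the surgery", and STUDY DESIGN repeats that the monitor collects data continuously. The staff duties described there cover noting the IAP points and taking the lactate samples. Urine is not mentioned. Worksheet entries go into the database and the worksheet is then destroyed. No export of the monitor's own record is described. The analysis paragraph gives a t-test or Wilcoxon comparison of groups and does not describe a within-patient change.

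**The concern.** A decrease needs a rate to decrease from. Lactate and IAP each have a named baseline, and urine output does not. Whoever analyses Hypothesis 3 must therefore choose a reference after the event, and the two obvious choices both cause trouble.

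- **Intraoperative urine only, as in step 9.** There is no pre-insufflation value. A comparison of early with late surgery, or of insufflation with the period after desufflation, answers a different question.
- **Volume counted from catheter insertion.** The first interval can contain urine that was in the bladder before monitoring began. Later intervals then look lower even if the kidneys produced urine at a constant rate. The error runs in the direction that Hypothesis 3 predicts.

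Hypothesis 4 uses the same change and inherits the problem. The study is a pilot meant to pick out findings for larger work, so a drainage artefact read as reduced urine production would be a false lead of the kind a pilot should avoid.

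**Working it through.** The plan gives no figure for urine output, so there is none to reproduce. The check has four parts.

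**1. Order of steps against the three measurements**

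| Period | IAP | Lactate | Urine output |
|---|---|---|---|
| Before the procedure (steps 6-7) | named | named | monitor connected, not named |
| During surgery (step 9) | one point | every 10 minutes | named, no times |
| After desufflation and closure (steps 10-11) | named | no separate entry | monitor connected, not named |
| Extubation (steps 12-13) | named | named | monitor connected until removal |
| 30 and 60 minutes after surgery (step 14) | none | named | catheter out |

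A pre-insufflation window and a post-desufflation window both exist physically. Neither is defined for urine. At the last two lactate times no catheter urine is possible: 25 patients x 2 = 50 planned lactates without a urine partner.

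**2. Expected new urine in the baseline window**

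Assumptions, none of them in the documents: weight 90-110 kg, true rate 0.5-1.0 mL/kg/h, window 10 minutes.

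Volume = weight x rate x minutes / 60.

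- Low: 90 x 0.5 x 10 / 60 = 7.5 mL
- High: 110 x 1.0 x 10 / 60 = 18.3 mL

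For windows of 5 to 20 minutes the range is 90 x 0.5 x 5 / 60 = 3.8 mL to 110 x 1.0 x 20 / 60 = 36.7 mL. In hourly terms the assumed true rate is 90 x 0.5 = 45 mL/h to 110 x 1.0 = 110 mL/h.

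**3. Effect of residual bladder urine**

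Assume a residual of V mL that drains wholly inside a counted 10-minute window. The added apparent rate is V x 60 / 10 = 6V mL/h.

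| V (assumed) | Added to first-interval rate |
|---|---|
| 50 mL | 300 mL/h |
| 100 mL | 600 mL/h |
| 200 mL | 1,200 mL/h |

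If urine production does not change at all, the later rate minus the first rate is then -300 to -1,200 mL/h, against a true rate of 45-110 mL/h. In volume, the residual is between 50 / 18.3 = 2.7 and 200 / 7.5 = 26.7 times the new urine in that window. If the bladder has emptied before counting starts, V = 0 and the bias is zero. The size therefore depends on where the count begins, which the plan does not say.

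**4. Precision of a properly defined paired change**

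The half-width of the 95% confidence interval for a mean paired difference is t(0.975, n-1) / sqrt(n), in units of the SD of the within-patient change.

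- n = 25: 2.064 / 5 = 0.41 SD
- n = 20 (assumed, if some baselines are unusable): 2.093 / 4.472 = 0.47 SD

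The documents give no SD, so this cannot be converted to mL/h.

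**The case against.** A reader might infer that no decrease can be estimated at all, or that none of the 25 patients will have a pre-insufflation urine rate. The documents do not support either statement. The catheter is connected to the monitor before baseline and before surgery, collection is continuous, and the catheter stays in through desufflation and closure until extubation. If the device record is kept, a contrast of insufflation with the preceding or following period can be derived. The steps are also only a summary, and the data collection worksheet is not in the documents, so it may contain urine fields.

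Catheter removal should not be overstated either. The protocol asks about changes induced by insufflation, and those occur while the catheter is in place. The 30- and 60-minute lactates are not a mistake, since they can describe lactate recovery. They matter for Hypothesis 4 only if someone tries to pair them with urine.

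The two difficulties, no reference and a contaminated reference, are alternatives. They cannot both apply in full. Because the catheter is placed to decompress the bladder, much of the residual may drain before surgery begins. The 50-200 mL and the 10 minutes are assumptions. The study is also a small observational pilot that disclaims practice-changing conclusions.

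All of this stands, and it limits the point without removing it. Continuous capture helps only if the record is retained and the windows are marked. The plan describes neither for urine, while it destroys the worksheets after transfer and all study data at the end.

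**Conclusion.** The point holds as a gap in definition and recording. As planned, the urine part of Hypothesis 3 and the urine change in Hypothesis 4 have no defined pre-insufflation reference. A fall remains derivable from the monitor's data if those data are kept. If the rate is counted from catheter insertion, the bias favours the predicted fall. Its size is conditional: zero if the bladder has emptied before counting starts, and 300-1,200 mL/h if 50-200 mL drains within a counted 10-minute window. The absence of a urine entry at step 7, of urine time points and of a change definition rests on the text alone. The size of the bias rests on assumed residual volume and drainage time. This is an inexpensive improvement worth making before enrolment, because the baseline window occurs once per patient. It is not a finding that the study cannot address urine output.

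**What to change.** 1. **Baseline.** Add urine output to step 7. Mark the monitor's recorded volume once initial drainage has settled, then log the volume and elapsed time from that mark to first insufflation. Do this in the time already available, without delaying surgery.
2. **Later windows.** Log or export volume and time for the insufflation period and for the period from desufflation to catheter removal, with readings aligned to the lactate times. State the unit (mL/kg/h is one suitable choice). Add urine to the staff recording duties and keep the device data until the analysis is complete.
3. **Hypothesis 3.** Define the urine effect as the paired within-patient difference, insufflation rate minus baseline rate. Report it with a 95% confidence interval and the length of each patient's baseline window.
4. **Hypothesis 4.** Limit lactate-urine pairs to samples taken before catheter removal. Use the 30- and 60-minute lactates for lactate recovery only.

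The cost is a few worksheet lines or a device export, using equipment already connected at step 6. The drawback is a short baseline window that may hold only about 4-37 mL under the assumptions above, so individual baseline rates will be noisy. No change to catheter management is proposed.
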